#### **6.13.8.2.2. Analyses of ADA Effects on Efficacy**

The impact of ADA effect on efficacy will be done for Long-Term Ixekizumab Efficacy Population. The proportion of patients achieving ASAS 20, ASAS 40 and ASDAS <2.1 will be summarized by TE-ADA status at Week 64 and Week 104. Similarly, summary statistics will be provided by NAb status and TE-ADA titer group, respectively.

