
 • To evaluate the development of anti-ixekizumab antibodies and its impact on the efficacy of ixekizumab 	
 • Efficacy response rates listed below at Weeks 64 and 104 by treatment-emergent anti-drug antibody (TE-ADA) status and by neutralizing anti-drug antibody (NAb) status: 
 ◦ Proportion of patients achieving ASAS40 ◦ Proportion of patients achieving ASAS20 ◦ Proportion of patients achieving ASDAS inactive disease

CCI

5. Study Design

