9.1.2. Secondary Efficacy Assessments

9.1.2.1. Ankylosing Spondylitis Disease Activity Score

Four disease activity states have been defined by ASAS consensus (Machado et al. 2011c):

- ASDAS < 1.3 defines inactive disease
- $1.3 \leq \text{ASDAS} < 2.1$ defines moderate disease activity
- $2.1 \leq \text{ASDAS} \leq 3.5$ defines high disease activity
- ASDAS > 3.5 defines very high disease activity

Secondary efficacy assessments will include evaluation of patients who meet the criteria for inactive disease (ASDAS <1.3; Machado et al. 2011c), clinically important improvement (defined as change ≥ 1.1 units), and major improvement (defined as change ≥ 2.0 units; Machado et al. 2011b).

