10.3.1.5.2. Modified Nonresponder Imputation for Clinical Response

Analysis of categorical efficacy and health outcome variables for long-term ixekizumab treatment analysis will be assessed using a modified nonresponder imputation (mNRI) method. Patients will be considered as nonresponders if they discontinue study drug due to a flare, an AE, or lack of efficacy. For patients discontinuing study drug for any other reason, the data will be imputed using multiple imputation method (as described in Section 10.3.1.5.4). Patients without at least 1 observation will also be defined as nonresponders for the mNRI analysis.

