#### **6.1.2.2. Long-Term Ixekizumab Treatment Efficacy Population**

Efficacy and health outcome data will be summarized for the Long-Term Ixekizumab Treatment Efficacy Population (see definition in Section 6.1.1) from Week 0 in the originating study to the visit at Week 64 and Week 104, respectively, in RHYB. For patients who were escalated from ixekizumab 80 mg Q4W to ixekizumab 80 mg Q2W after Week 64, only data while on ixekizumab 80 mg Q4W will be included. If the patient early terminates the originally assigned treatment (including retreatment and escalation) prior to Week 104, then the modified nonresponder imputation (mNRI) method will be applied for categorical endpoints, and modified baseline observation carried forward (mBOCF) will be applied for continuous endpoints from the early termination visit through Week 104.

The long-term treatment effect on a categorical variable is measured by the proportion of patients who have achieved or maintained a response (see algorithm in [Table RHY.6.4](#)) through Week 64 and Week 104, respectively, and the long-term treatment effect on a continuous variable is measured by change (or percent improvement) from baseline in the originating study.

The long-term treatment effect in categorical variables using observed cases, and continuous variables using observed cases and mBOCF will be summarized (as described in Section [6.1](#)) by treatment group (see [Table RHY.6.1](#)) at each scheduled visit from Week 0 in originating study. An alternative method to handle the missing data after Week 64 for the period of Week 0 in the originating study to Week 104 in RHY, mNRI method will be applied for categorical variables and mixed model for repeated measures (MMRM) will be applied for continuous variables. Data will also be summarized graphically using the response rate for categorical variables and mean for continuous variables by group at each scheduled visit. The time points during the Extension Period (Period 2) will follow the scheduled visits for group A patients with between-visits-interval of 8 weeks.

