### 6.3.2. Modified Nonresponder Imputation

Analysis of categorical efficacy and health outcome variables for long-term ixekizumab treatment analysis will be assessed using an mNRI method. Patients will be considered as nonresponders if they receive retreatment due to a flare or discontinue study drug due to AE (including death) or lack of efficacy. For patients discontinuing study drug for any other reason, the data will be imputed using the multiple imputation (MI) method (as described in Section 6.3.4).

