Long-Term Ixekizumab Treatment Efficacy Population (to evaluate long-term treatment effect through Week 104)	For other secondary objectives: • ASDAS: Clinically-important improvement, Major improvement, Inactive disease, ASDAS <2.1 • ASAS20, • ASAS40, • ASAS5/6, • ASAS partial remission, • BASDAI50. • Enthesitis: MASES = 0, SPARCC = 0. For patients with MASES >0 and SPARCC >0, respectively, at baseline from originating study • Peripheral arthritis: TJC = 0 SJC = 0 For patients with TJC >0 and SJC >0, respectively, at baseline from originating study • Anterior uveitis or uveitis flare: Crude and exposure-adjusted incidence rates for patients with anterior uveitis	Descriptive statistics (for categorical variables with observed and mNRI through Week 104)	IXE80Q2W a IXE80Q4W a Total IXE at each scheduled visit from Week 0 in originating study to Week 64 and Week 104, respectively.
Long-Term Ixekizumab Treatment Efficacy Population (to evaluate long-term treatment effect through Week 64 and Week 104, respectively)	For other secondary objectives: Change from Baseline for: • ASAS - 4 components: Patient global, Spinal pain, Function, Inflammation. • ASDAS • BASDAI, • BASFI,	Descriptive statistics (for continuous variables with mBOCF and MMRM through Week 104)	IXE80Q2W a IXE80Q4W a Total IXE a at each scheduled visit from Week 0 in originating study to Week 64 and Week 104, respectively.

Population	Variable	Analysis Method (Section 6.1)	Comparison/Time Point
	
 
BASMI:           
 
Linear,
 
Chest expansion and
 
Occiput to wall distance,
 
 
 
Enthesitis:           
 
MASES,
 
SPARCC.
 
 
 
 
For patients with MASES >0 and SPARCC >0, respectively, at baseline from originating study
 
 
Peripheral Arthritis Severity           
 
TJC
 
SJC
 
 
 
 
For patients with TJC >0 and SJC >0, respectively, at baseline from originating study
 
 
CRP
 
		

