	
Other secondary outcomes:
 
Treatment group by TE-ADA, NAb and Titer group on:
 
 
ASAS20,
 
ASAS40,
 
ASDAS <2.1
 
	
Descriptive statistics (observed):
 
Number and proportion of patients achieving response of interest.
 
No inferential statistics.
	
IXE80Q2W, IXE80Q4W, Total IXE by TE-ADA status, NAb status, and titer group, respectively. At Week 64 and Week 104

Flare Population with Retreatment (to assess the efficacy of retreatment)
	
For other secondary objectives:
 
 
ASAS20,
 
ASAS40,
 
ASAS5/6,
 
ASAS partial remission,
 
ASDAS:           
 
ASDAS<1.3
 
ASDAS<2.1
 
 
 
Clinically-important improvement
 
Major improvement,
 
Inactive disease
 
	
Descriptive statistics (for categorical variables) for within 16 weeks of ixekizumab retreatment.
 
Kaplan-Meier estimates of the proportion of patient who regain response on the variables of interest at each post-retreatment interval up to 40 weeks.
	
PBO/IXE80Q2W, PBO/IXE80Q4W PBO/IXE IXE80Q2W/ IXE80Q2W IXE80Q4W/ IXE80Q4W IXE/IXE
 
no inferential statistics within 16 weeks of Ixekizumab retreatment and at each retreatment interval (4 weeks, 8 weeks, etc.) up to 40 weeks.

Abbreviations: ASAS = Assessment of Spondyloarthritis International Society; ASDAS = Ankylosing Spondylitis Disease Activity Score; BASDAI = Bath Ankylosing Spondylitis Disease Activity Index; BASFI = Bath Ankylosing Spondylitis Functional Index; BASMI = Bath Ankylosing Spondylitis Metrology Index; Baseline=baseline from the originating study RHBV, RHBW or RHBX; CRP = C-reactive protein; ITT = intent-to-treat; IXE-Structure = patients from Ixekizumab Structure Population; IXE80Q2W = ixekizumab 80 mg every 2 weeks; IXE80Q4W = ixekizumab 80 mg every 4 weeks; MASES = Maastricht Ankylosing Spondylitis Enthesitis Score; mBOCF = modified baseline observation carried forward; MMRM = mixed model for repeated measures; mNRI = modified nonresponder imputation; NRI = nonresponder imputation; SJC = swollen joint count; TJC = tender joint count; Total IXE = IXE80Q2W and IXE80Q4W combined; RW = randomized withdrawal.

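### The antibody-versus-efficacy analysis replaces the protocol's ASDAS inactive disease with ASDAS <2.1 and uses observed cases only, out of step with the unsplit table at Week 104

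*SAP*

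**What the plan says.** **Endpoint.** Protocol Section 4 (Table RHBY.1), like the Synopsis, gives three response rates for this objective, by TE-ADA and NAb status at Weeks 64 and 104: ASAS40, ASAS20 and "Proportion of patients achieving ASDAS inactive disease". Protocol 9.1.2.1 fixes the threshold: "ASDAS < 1.3 defines inactive disease". SAP 6.13.8.2.2 has a different third endpoint: "The proportion of patients achieving ASAS 20, ASAS 40 and ASDAS <2.1 will be summarized by TE-ADA status at Week 64 and Week 104". SAP Section 4 and the antibody rows of Table RHBY.6.5 agree with 6.13.8.2.2.

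**Missing data.** In Table RHBY.6.5 the method for the TE-ADA, NAb and titer rows begins "Descriptive statistics (observed", and no imputation is listed. For the same Long-Term Ixekizumab Treatment Efficacy Population, the entry covering ASAS20, ASAS40, ASDAS <2.1 and inactive disease reads "Descriptive statistics (for categorical variables with observed and mNRI through Week 104". Protocol 10.3.1.5.2 says that long-term categorical variables will be "assessed using a modified nonresponder imputation (mNRI) method". SAP 6.3.2 classes patients as "nonresponders if they receive retreatment due to a flare or discontinue study drug due to AE (including death) or lack of efficacy"; those who stop for other reasons are multiply imputed. SAP 6.1.2.2 applies mNRI once assigned treatment ends early, and names retreatment and escalation as such endings. For patients escalated after Week 64 it adds that "only data while on ixekizumab 80 mg Q4W will be included".

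**The concern.** The objective asks whether antibodies reduce efficacy. Two features of the SAP make the planned table a weaker answer than the protocol promised.

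First, the table does not report one of the three endpoints that the protocol named. For the Period 2, retreatment and long-term objectives, the SAP adds ASDAS <2.1 and keeps inactive disease. Only the antibody objective loses it, although the variable is already derived and is summarized for these same patients.

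Second, loss of efficacy can show itself as stopping treatment or as escalation. With observed cases at Week 104, a patient with such an outcome has no value and leaves the denominator. In the unsplit table under mNRI, the same patient is meant to be carried. The antibody categories would then not add up to the unsplit mNRI result, and a difference between categories could be understated.

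**Working it through.** The documents give no antibody incidence, response rate, dropout rate or power for this analysis, so there is no stated figure to reproduce. The factual part is a comparison of texts. The arithmetic uses assumed values to show what the choices can do.

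**1. Who leaves the antibody split at Week 104**

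| Patient after Week 64 | Antibody rows (observed) | Unsplit table (mNRI) |
|---|---|---|
| Stops for adverse event or lack of efficacy | absent | nonresponder |
| Stops for another reason | absent | multiply imputed |
| Escalated from Q4W to Q2W | absent (later data excluded) | mNRI applies by 6.1.2.2, but 6.3.2 does not say how escalation is classed |
| Retreated for flare | not stated whether later observed values count | nonresponder |
| Loses response, stays on regimen | nonresponder | nonresponder |

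**2. How many might be lost**

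Protocol 5.2 cites about 85% one-year retention, from ixekizumab psoriasis studies and one secukinumab study. Applying it here is an assumption.

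- Week 64 to Week 104 (40 weeks): 1 − 0.85^(40/52) = 1 − 0.88 = 0.12, about 12%.
- Two full years: 1 − 0.85² = 1 − 0.7225 = 0.2775, about 28%.

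The population in SAP 6.1.1 is defined by the same regimen through Week 64, so the 40-week figure fits Week 104 better and 28% is an upper bound. Both are before escalation or retreatment is counted.

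**3. What observed cases do to a difference**

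Let r be the true response rate and f the share of nonresponders who are absent, with all responders present. The observed-case rate is r / [r + (1 − r)(1 − f)], and the overall loss in the group is (1 − r)f. Assume r = 0.60 in antibody-negative and 0.40 in antibody-positive patients. Counting every absent nonresponder as a failure returns the true gap of 20 points.

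| f, negative / positive | Overall loss, negative / positive | Observed rate, negative / positive | Gap (points) |
|---|---|---|---|
| 0.3 / 0.3 | 12% / 18% | 0.682 / 0.488 | 19.4 |
| 0.1 / 0.3 | 4% / 18% | 0.625 / 0.488 | 13.7 |
| 0.2 / 0.5 | 8% / 30% | 0.652 / 0.571 | 8.1 |
| 0.1 / 0.6 | 4% / 36% | 0.625 / 0.625 | 0.0 |
| 0.3 / 0.1 | 12% / 6% | 0.682 / 0.426 | 25.6 |

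Row two worked through: 0.6/(0.6 + 0.4×0.9) = 0.6/0.96 = 0.625; 0.4/(0.4 + 0.6×0.7) = 0.4/0.82 = 0.488.

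Equal loss of nonresponders barely moves the gap. It shrinks clearly only when antibody-positive nonresponders leave more often, and it grows when the imbalance is reversed.

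**4. What the cut-off does**

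Treat ASDAS as normal, with mean 1.5 to 2.3 in antibody-negative patients, SD 0.8 or 1.0, and worsening of 0.3 or 0.5 in antibody-positive patients (20 combinations, all assumed). The gap is Φ((t − μ)/σ) − Φ((t − μ − δ)/σ), where t is the cut-off, μ the mean, σ the SD and δ the worsening. With μ = 1.9, σ = 0.8 and δ = 0.3:

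- t = 1.3: 0.227 against 0.130, a gap of 9.6 points.
- t = 2.1: 0.599 against 0.450, a gap of 14.8 points.

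Over all combinations the gap is 5.4 to 21.1 points at <1.3 and 10.8 to 24.5 points at <2.1. It is larger at <2.1 in 18 of the 20.

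**The case against.** Several points on the other side are sound.

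- **Observed cases are not foreign to this population.** SAP 6.1.2.2 summarizes categorical variables by observed cases and offers mNRI as the alternative for missing data after Week 64. SAP 6.14.1 uses observed cases for other subgroup displays, but at Week 64. This confines the inconsistency to Week 104; it does not remove it there.
- **ASDAS 2.1 is a meaningful boundary in this trial.** It is part of the flare definition, and ASAS20 and ASAS40 are retained. That justifies reporting <2.1, but not leaving out the endpoint that the protocol named.
- **The analysis is descriptive.** It serves one other-secondary objective and has no role in the multiplicity scheme. Protocol 10.3.1 lets non-principal changes be justified in the study report, and Protocol 10.3.6.3 leaves the evaluation flexible. Parts of the SAP are redacted, so a reason may exist there. This limits the weight of the point.
- **mNRI is not neutral.** Patients who stop for other reasons are imputed as though they had continued, and neither description of the imputation model (Protocol 10.3.1.5.4, SAP 6.3.4) includes antibody status. Leaving it out can itself pull the categories together. This stands and shapes the fix.
- **The larger selection happens earlier.** SAP 6.1.1 requires the same regimen through Week 64 and excludes patients retreated in Period 2. mNRI does not bring them back.

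A reader might infer that the SAP hides an antibody effect, or that the looser cut-off biases the comparison towards no difference. The documents support neither. They do not say which antibody category loses more patients, and the cut-off calculation mostly points the other way. Nor do all patients who lose response disappear: those who stay on regimen count as nonresponders.

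**Conclusion.** Two facts rest on the text alone. The SAP replaces the protocol's third antibody-efficacy endpoint without a visible reason, and it limits the antibody rows to observed cases where the same variables in the same population also get mNRI through Week 104.

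The consequence is a risk of attenuation at Week 104, not a demonstrated bias. It arises if treatment stops and escalations are more frequent among antibody-positive nonresponders. The direction and size are unknown. An assumed 20-point gap becomes 0 to 25.6 points, and the zero case needs 36% of antibody-positive patients to be lost, all of them nonresponders. The share lost after Week 64 is about 12% on the assumed retention rate, with 28% as an upper bound. The endpoint change is a departure from the protocol to be repaired or explained; it is not a mechanism that conceals an effect.

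**What to change.** 1. In SAP Section 4, Table RHBY.6.5 and 6.13.8.2.2, restore ASDAS inactive disease (<1.3) and keep ASDAS <2.1 beside it.
2. At Week 104, report the TE-ADA, NAb and titer rows with mNRI as well as observed cases. State how escalated patients are classed, since 6.3.2 does not name them, and include antibody status in the imputation model.
3. For each antibody category, show how many patients left, were retreated or were escalated before the visit.
4. Record as a limitation that the population already excludes patients retreated in Period 2, whom mNRI does not restore.

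The cost is SAP wording and a little more programming: the ASDAS variable and the mNRI method already exist for this population, and only the imputation model needs an added term. Response figures may come out slightly less favourable.

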#### **6.13.8.2.3. Analyses of Treatment-Emergent ADA on Specific Adverse Events**

The analyses of TE-ADA on specific adverse events will be conducted on all evaluable patients within the Lead-In Period Safety Population during Combined Periods 1 and 2, and Combined Periods 1, 2, and 3, and for RW Safety Population during Period 2. For Lead-In Period Safety Population during the combined periods, all data are included regardless of treatment changes.

Adverse events of special interest, allergic reaction/hypersensitivity (anaphylaxis and non-anaphylaxis) and of injection-site reactions, will be included in an assessment of AE to TE-ADA over time. Timing of an AE will be taken to be the reported AE start date.

For each TE-ADA status dichotomous variable (as defined in [Table RHBY.6.10](#)), patients will be categorized according to whether they were (i) always in lesser-TE-ADA status postbaseline or (ii) at least once in greater-TE-ADA status postbaseline. For each AESI, within the time-varying TE-ADA status groups, a summary will be provided of the number of patients who had no event, events only while in lesser-TE-ADA status for group (i), or – for group (ii) – at least 1 event while in greater-TE-ADA status.

Additionally, summaries will be provided of the total number of AESI events (with unique start dates) by time-varying TE-ADA status groups at the event date. The summaries will aggregate time respectively in greater-TE-ADA status and in lesser-TE-ADA status, along with the event rates (rates per 100 patient-years) relative to those aggregate times.

By-patient listings will be provided of patients with TE-ADA who experience a treatment-emergent allergic reaction/hypersensitivity reaction or an injection site reaction.

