Visit No (Group B) ^c	V1 ^a	V2	V3	V4	V505 ^c	V506	V507	V508	V509	V510	V511	V512	V513	V514	V515	V516	V517	V518	V519	ETV		
Study Week	W0	W8	W16	W20	W24	W28	W32	W36	W40	W44	W48	W52	W56	W60	W64	W76	W88	W100	W104			
Study Day	^b	56 ± 5d	112 ± 5d	140 ± 5d	168 ± 5d	196 ± 5d	224 ± 5d	252 ± 5d	280 ± 5d	308 ± 5d	336 ± 5d	364 ± 5d	392 ± 5d	420 ± 5d	448 ± 5d	532 ± 5d	616 ± 5d	700 ± 5d	728 ± 5d			
Urinalysis	X				X							X					X			X	X	
CCI																						
Immunogenicity testing ^{v,w}	X				X							X				X		X		X	X	X
PK sampling ^{v,x}	X				X							X				X		X		X	X	

Post-Treatment Follow-Up for Patients Discontinuing Treatment (Period 4) ^y			
	Required Follow-Up Visits		As-Needed Follow-Up Visits
Visit No	V801	V802	V803 and Onwards
Study Week	LV + 4W	LV + 12W	LV + 24 W
Study Day	±14d	±14d	±14d
Concomitant medications	X	X	X
Vital signs (BP and pulse) ^e	X	X	X
Weight ^f	X	X	X
Preexisting conditions and medical history ^j	X	X	X
Adverse events	X	X	X
C-SSRS	X	X	X
Self-Harm Supplement Form ^o	X	X	X
QIDS-SR16	X	X	X
HBV DNA ^q	X	X	
Serum chemistry	X	X	X
Hematology	X	X	X
CCI			
Immunogenicity testing ^{v,w}		X	
PK sampling ^{v,x}		X	

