10.3.6.3. Immunogenicity

The analyses of anti-drug antibody (ADA) effects will be conducted on all evaluable patients within the defined Randomized Withdrawal Safety Population. Evaluable patients will be defined as either: a) patients with an evaluable baseline sample and at least 1 evaluable postbaseline sample (i.e., sample after administration of study drug); or b) patients with no evaluable baseline sample whose evaluable postbaseline samples were all ADA negative.

A treatment-emergent positive anti-drug antibody (TE-ADA+) patient will be defined as any occurrence of a greater than or equal to 4-fold or 2 dilution increase in immunogenicity titer over the baseline titer. This is equivalent to an increase in titer to $\geq 1:10$, in the case of a negative result at baseline.

The frequency and percentage (incidence) of patients with positive, negative, or inconclusive ADA at baseline and postbaseline (and NAbs at baseline and postbaseline) will be summarized by treatment group. Patients who are TE-ADA positive, TE-ADA persistent positive, and TE-ADA transient positive will also be summarized.

The potential impact of immunogenicity on efficacy responses will be evaluated, as appropriate.

Assessment of immunogenicity with respect to safety will include comparison of patients who experience treatment-emergent adverse event (TEAEs) of systemic allergy/hypersensitivity and of injection-site reactions and who also develop treatment-emergent anti-ixekizumab antibody positivity with patients who experience the same types of TEAEs but who remain treatment-emergent anti-ixekizumab antibody negative. Anti-ixekizumab antibody titers will also be evaluated in anti-ixekizumab antibody positive patients who experience these events.

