**Table RHBY.6.10. TE-ADA Status Dichotomous Variables for AE Analysis**

TE-ADA Status Dichotomous Variable	Greater-TE-ADA Status	Lesser-TE-ADA Status
TE-ADA positive	TE-ADA positive	not TE-ADA positive
TE-ADA moderate-to-high	TE-ADA positive with moderate titer or high titer	not TE-ADA positive, or TE-ADA positive with low titer
TE-ADA high status	TE-ADA positive with high titer	not TE-ADA positive, or TE-ADA positive with low or moderate titer

Note: For purpose of this analysis, TE-ADA Inconclusive is taken to be “not TE-ADA positive.”

Note: A TE-ADA low is defined as a TE-ADA positive with a titer value  $<1:160$ ; a TE-ADA moderate is defined as a TE-ADA positive with a titer value  $\geq 1:160$  and  $<1:1,280$ ; and a TE-ADA high is defined as a TE-ADA positive with a titer value  $\geq 1:1,280$ .

For each TE-ADA status dichotomous variable, a time-varying TE-ADA status will be computed. For those time points when there is no TE-ADA sample is collected, the TE-ADA status will be derived as: at time  $t$ , the TE-ADA status is taken to be the highest of the TE-ADA values bracketing time  $t$ . More formally, the TE-ADA status at time  $t$  is given by the greater of (a) the TE-ADA status at the most-recent postbaseline measurement prior to  $t$ , and (b) the TE-ADA status at the first TE-ADA postbaseline measurement at or after time  $t$ . In this computation, “greater” is given by the greater-TE-ADA status of Table RHBY.6.10. If there is no value satisfying criterion (a), then the value (b) is used. Similarly, if there is no value (b), then the value (a) is used.

For each analysis period and each TE-ADA status dichotomous variable, patients will be categorized according to whether they were (i) always in lesser-TE-ADA status postbaseline or (ii) at least once in the greater-TE-ADA status postbaseline.

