#### **6.13.8.2.1. Analyses of Characteristics of ADA Immune Response**

The analyses of ADA effects will be conducted on all evaluable patients within the Lead-In Period Safety Population during Combined Periods 1 and 2, and Combined Periods 1, 2, and 3 and with RW Safety Population during Period 2.

Evaluable patients will be identified as positive, negative, or inconclusive for ADA, according to the definitions provided in Section [6.13.8.1.2](#).

The frequency and percentage (incidence) of patients will be summarized by treatment group for the TE-ADA status groups and the time-varying TE-ADA status groups. Scheduled visits, unscheduled visits, and repeat measurements will be included. This analysis will also be done for Group A and Group B Patients separately during Period 1.

In addition, the overall frequency and percentage (incidence) of patients will be summarized for the patients who are baseline ADA positive by TE-ADA status groups. For those patients who are TE-ADA positive, a summary of titer values and the proportion of patients who are NAb positive will also be provided.

For each TE-ADA status dichotomous variable (as defined in [Table RHBY.6.10](#)), summaries will be provided of the total postbaseline time in the greater-TE-ADA status for patients who were at some point postbaseline in the greater-TE-ADA status group. Postbaseline time in the greater-TE-ADA status for each patient will be aggregated.

A by-patient listing to include treatment, visit date, visit, ADA result, TE-ADA result, NAb result, ADA titer value, ixekizumab concentration, ADA and NAb inconclusive results will also be provided, for patients with any 1 sample of ADA (or NAb) positive or inconclusive.

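### The patient count of allergic and injection-site reactions by antibody group has no category for antibody-developing patients whose reactions all fell in lesser-TE-ADA time

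*SAP*

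**What the plan says.** SAP 6.13.8.2 defines three dichotomous TE-ADA variables (Table RHBY.6.10), each with a greater and a lesser status. For each variable and analysis period, patients are sorted into (i) "always in lesser-TE-ADA status postbaseline or (ii) at least once in the greater-TE-ADA status postbaseline".

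Status varies over time. Between samples, "the TE-ADA status is taken to be the highest of the TE-ADA values bracketing time" t. If a sample exists on only one side of t, that sample's status is used. For the high-titer variable, lesser status means "not TE-ADA positive, or TE-ADA positive with low or moderate titer".

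SAP 6.13.8.2.3 applies this to allergic reactions/hypersensitivity and injection-site reactions. The patient-count summary has three categories: no event, then "events only while in lesser-TE-ADA status for group (i), or – for group (ii) – at least 1 event while in greater-TE-ADA status". The same section also plans event counts by status at the event date, rates per 100 patient-years over aggregated greater-status and lesser-status time, and by-patient listings of TE-ADA patients who have these reactions.

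Protocol 10.3.6.3 sets the purpose. It compares patients who have these events and "who also develop treatment-emergent anti-ixekizumab antibody positivity with patients who experience the same types of TEAEs but who remain" antibody negative.

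**The concern.** Being in the greater status at least once does not mean being in it throughout, so a group (ii) patient can have lesser-status follow-up and can react during it. The lesser-only category is tied to group (i), and the only with-event category for group (ii) requires an event in greater status. A group (ii) patient who reacted only in lesser-status time is in neither, and is not event-free.

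The two groups' with-event counts then rest on different observation windows: all follow-up for group (i), greater-status time alone for group (ii). A reader setting the two side by side would understate how many antibody-developing patients had a reaction. The protocol's comparison does not require the reaction to fall in antibody-positive time.

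**Working it through.** The plan states no figure to reproduce here. The question is whether the categories cover every patient who can occur.

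**Cross-classification.** Cross the two groups with the three possible event histories:

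| Event history | Group (i) | Group (ii) |
|---|---|---|
| No event | named | named |
| Events in lesser status only | named | **not named** |
| At least 1 event in greater status | impossible | named |

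Group (i) has no greater-status time, so five cells are possible. The text names four.

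**Can the unnamed cell occur under the bracketing rule?** Take two postbaseline samples, giving three intervals (before the first, between the two, after the second), each with or without an event. That is 2² × 2³ = 32 patterns.

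- Lesser then greater: the first interval is lesser, the other two greater. An event in the first interval only reaches the cell (1 pattern).
- Greater then lesser: the first two intervals are greater, the last lesser. An event in the last interval only reaches the cell (1 pattern).
- Greater at both: no lesser time (0 patterns).

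The total is 2 of 32. The same enumeration for three, four and five samples gives 11 of 128, 42 of 512 and 138 of 2048. The numbers of samples are assumptions, and these are counts of patterns, not probabilities. They show only that the cell is reachable each time. Bracketing shrinks the gap, because time between a lesser and a greater sample counts as greater, but time between two lesser samples stays lesser.

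**How much of one patient's follow-up can lie there?** The Protocol Section 2 schedule places immunogenicity samples at Weeks 0 and 24; the later columns are not readable in the extracted table. Suppose a patient is in lesser status at both and first reaches greater status at a later sample. Weeks 0 to 24 are then lesser. If Week 0 is the ADA baseline, the Week 24 value alone applies and the result is the same. Assuming full follow-up, the minimum share is:

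- Combined Periods 1 and 2: 24/64 = 37.5%
- Combined Periods 1, 2, and 3: 24/104 = 23.1%

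For a patient in greater status throughout, the share is 0%.

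**Other routes into the cell.** Protocol 9.4.9 calls for an extra sample after a potential systemic allergic reaction. If such samples feed the time-varying status, a lesser result just after the event, with a lesser one before it, fixes the event as lesser whatever the next scheduled sample shows. For the high-titer variable, a patient who reacts at moderate titer and reaches high titer only at a later, non-adjacent sample also falls in the cell.

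**Can the count be recovered?** Yes, if the no-event count is shown by group and group sizes are available. SAP 6.13.8.2.1 plans the latter: "The frequency and percentage (incidence) of patients will be summarized by treatment group for the TE-ADA status groups and the time-varying TE-ADA status groups". Then

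unnamed cell = group (ii) size − group (ii) no event − group (ii) with at least 1 event in greater status.

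**The case against.** The strongest reply is that nothing is lost from the report. Greater status in all three variables requires TE-ADA positivity, so every affected patient is TE-ADA positive and appears in the by-patient listing, which is not limited to greater-status time. The events also enter the event counts and the rates. This stands, and it limits the harm. However, a listing is not a tabulated count, and the rates count events, not patients.

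The three variables are nested, so a patient who reacts at low or moderate titer is missed only under a stricter variable and is still counted as a greater-status event under the TE-ADA-positive variable. That also stands, and it weakens the high-titer example. It does not help a patient who reacted before any positive sample and outside the bracketed interval.

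Focusing on reactions during antibody-positive time is defensible for an over-time assessment, and the protocol prescribes no category table. But group (ii)'s greater-status category already provides that focus, and naming the remaining cell takes nothing from it.

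Finally, the table shells are not in the documents. The produced table may print the lesser-only row for both groups, so one can be sure of the wording but not that patients would be dropped. That is fair. The 38% and 23% describe one hypothetical late converter's follow-up time; they are not shares of patients or events omitted.

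**Conclusion.** The concern holds, at minor severity. Followed literally, SAP 6.13.8.2.3 leaves one of five reachable cells without a category, and group (ii)'s with-event count covers less follow-up than group (i)'s. No other section supplies the category. The number of patients affected cannot be computed from the documents and may be zero.

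This is most likely a drafting slip. Group (i) patients are never in greater status, so restricting their events to lesser status adds nothing; the restriction separates patients only in group (ii), the group that the phrase excludes. No planned rate, test, listing or efficacy result is affected. The conclusion rests on the SAP wording and the bracketing rule; the percentages rest additionally on the late-converter scenario and full follow-up.

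**What to change.** In SAP 6.13.8.2.3, delete the three words *for group (i)* from the patient-count sentence. The lesser-only category then applies to both groups, and every evaluable patient falls in exactly one category. An any-event total per group is optional, since it equals group size minus the no-event count. Check that the table shell has a lesser-only cell for group (ii). The cost is three words and at most one more filled cell per table, with no new data.
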